8.0 ADVERSE EVENT REPORTING

8.1 Adverse event is any untoward medical occurrence that may present during treatment with a pharmaceutical product but which does not necessarily have a causal relationship with this treatment.

Adverse drug reaction is a response to a drug which is noxious and unintended and which occurs at doses normally used in man for prophylaxis, diagnosis, or therapy of disease or for the modification of physiologic function.

Assessing causal connections between agents and disease is fundamental to the understanding of adverse drug reactions. In general, a drug may be considered a contributory cause of an adverse event if, had the drug not been administered, 1) the event would not have happened at all, 2) the event would have occurred later than it actually did, or 3) the event would have been less severe.

The Investigator or physician designee is responsible for verifying and providing source documentation for all adverse events and assigning the attribution for each event for all subjects enrolled on the trial.

8.2 Adverse Events (AEs) will be evaluated according to the CTC AE version 4.0 and documented in medical record. Only unexpected AEs will be recorded in the Case Report Form (CRF). PDMS/CORe will be used as the electronic case report form for this protocol. Adverse events and protocol specific data will be entered into PDMS/CORe. Expected events during leukemia therapy are:

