Immuno-oncology (I-O) agents are associated with AEs that can differ in severity and duration than AEs caused by other therapeutic classes. Nivolumab is considered an immuno-oncology agent in this protocol. Early recognition and management of AEs associated with immuno-oncology agents may mitigate severe toxicity. Management algorithms have been developed to assist investigators in assessing and managing the following groups of AEs: Gastrointestinal, Renal, Pulmonary, Hepatic, Endocrinopathies, Skin, Neurological.

For subjects expected to require more than 4 weeks of corticosteroids or other immunosuppressants to manage an AE, consider recommendations provided in the algorithms. These algorithms are found in Appendix B of this protocol. The guidance provided in these algorithms should not replace the Investigator's medical judgment but should complement it.

5.5 Discontinuation Criteria:

Treatment should be permanently discontinued for the following:

- Any Grade 2 drug-related uveitis or eye pain or blurred vision that does not respond to topical therapy and does not improve to Grade 1 severity within the re-treatment period OR requires systemic treatment
- Any Grade 3 non-skin, drug-related adverse event lasting > 7 days, with the following exceptions for drug-related laboratory abnormalities, uveitis, pneumonitis, bronchospasm, diarrhea, colitis, neurologic adverse event, hypersensitivity reactions, and infusion reactions:
 - Grade 3 drug-related uveitis, pneumonitis, bronchospasm, diarrhea, colitis, neurologic adverse event, hypersensitivity reaction, or infusion reaction **of any duration** requires discontinuation
 - Grade 3 drug-related laboratory abnormalities do not require treatment discontinuation except those noted below:
 - Grade 3 drug-related thrombocytopenia > 7 days or associated with bleeding requires discontinuation
 - Grade 3 drug-related ALT, AST or total bilirubin require discontinuation:
- Any Grade 4 drug-related adverse event or laboratory abnormality, except for the following events which do not require discontinuation:
 - Isolated Grade 4 amylase or lipase abnormalities that are not associated with symptoms or clinical manifestations of pancreatitis and decrease to < Grade 4 within 1 week of onset.

- Isolated Grade 4 electrolyte imbalances/abnormalities that are not associated with clinical sequelae and are corrected with supplementation/appropriate management within 72 hours of their onset

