8.2.1 Myelosuppression related events (due to disease or leukemia therapy)

8.2.1.1 febrile or infection episodes not requiring management in the intensive care unit

8.2.1.2 epistaxis or bleeding except for catastrophic CNS or pulmonary hemorrhage

8.2.1.3 anemia, neutropenia, lymphopenia, thrombocytopenia, leukopenia

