8.2.2 Disease Related Events

8.2.2.1 Symptoms associated with anemia

8.2.2.1.1 fatigue

8.2.2.1.2 weakness

8.2.2.1.3 shortness of breath

8.2.2.2 electrolyte abnormalities (sodium, potassium, bicarbonate, CO₂, magnesium)

8.2.2.3 chemistry abnormalities (LDH, phosphorus, calcium, BUN, protein, albumin, uric acid, alkaline phosphatase, glucose)

8.2.2.4 coagulation abnormalities

8.2.2.5 disease specific therapy (induction, maintenance, salvage, or stem cell therapy)

8.2.2.6 alopecia

8.2.2.7 bone, joint, or muscle pain

8.2.2.8 liver function test abnormalities associated with infection or disease progression

8.2.2.9 disease progression

8.2.2.10 abnormal hematologic values

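### Section 8.2 keeps listed expected events off the CRF with no explicit exception for events attributed to nivolumab, so CRF data for the toxicity objective could be incomplete

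*Combined protocol and SAP*

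**What the plan says.** Secondary objective 5 (section 1.2) is the toxicity profile of nivolumab in AML patients in remission. Three provisions in section 8 bear on the data for it.

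- Section 8.1 makes the investigator or designee responsible for "verifying and providing source documentation for all adverse events and assigning the attribution for each event". Section 8.2 adds that AEs are graded by CTCAE version 4.0 and documented in the medical record.
- Section 8.2 then narrows what leaves the medical record: "Only unexpected AEs will be recorded in the Case Report Form (CRF". It names PDMS/CORe as the electronic CRF and continues, without any limit, "Adverse events and protocol specific data will be entered into PDMS/CORe".
- Sections 8.2.1 to 8.2.4 list the expected events for leukemia therapy. One group is headed "Myelosuppression related events (due to disease or leukemia therapy". Another is headed as disease-related and contains "8.2.2.1 Symptoms associated with anemia" (fatigue, weakness, shortness of breath), "8.2.2.2 electrolyte abnormalities (sodium, potassium, bicarbonate" and further electrolytes, and "8.2.2.7 bone, joint, or muscle pain". Liver tests are listed only with infection or progression, and rash only with antibiotics.

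Section 8.3 puts the worst chemistry value per course on the CRF and keeps hematology values off it. Section 8.4 requires all SAEs to be reported, expected or not and whatever their attribution. Section 9.0 defines the monitored toxicity by relatedness, clinical significance, grade and non-hematologic type. It does not say which data source supplies the counts.

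**The concern.** Entry on the CRF turns on whether an event is on the list. Attribution to the study drug is collected, but it does not decide entry. That is awkward when the objective is the toxicity profile of that drug, and when the list was written for leukemia therapy in general.

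Two listed items have no limit by cause beyond their group heading: musculoskeletal pain, and electrolyte and chemistry abnormalities. The protocol treats both as possible drug effects. Section 2.4.2.3 reports treatment-related arthralgia. Section 5.5 addresses "Any Grade 4 drug-related adverse event or laboratory abnormality, except for the following events which do not require discontinuation", and the exceptions that follow include isolated grade 4 electrolyte abnormalities.

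At stake is the completeness of the CRF dataset for objective 5 in a single-arm study of at most 30 patients. Two coordinators could each follow 8.2 in good faith and enter different events.

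**Working it through.** **Step 1: is a nivolumab-attributed listed event on the CRF?** The relevant text gives three answers.

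- The rule on unexpected AEs, with the list: no, if the event is a listed type.
- The headings read strictly by cause: yes, because an event attributed to nivolumab is not disease-related. But 8.2 does not state this. The phrase leukemia therapy is not defined. Sections 2.6 and 9.0 describe nivolumab as maintenance therapy, and item 8.2.2.5 names maintenance among disease-specific therapies, so the study drug is not clearly outside the list.
- The unqualified sentence on PDMS/CORe: yes, for all AEs.

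Section 8.2 does not settle the question, and nothing in 8.3 or 8.4 settles it for non-serious events.

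**Step 2: what do the other routes recover?**

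- Source records: every AE, with grade and attribution.
- SAE reporting (8.4): serious events, expected or not.
- Worst chemistry value (8.3): severity of chemistry events, and of electrolyte events if these count as chemical values. It makes no provision for attribution.
- Pain has no laboratory value, so 8.3 recovers nothing for it.

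What remains exposed is mainly non-serious bone, joint or muscle pain attributed to nivolumab, plus the attribution of electrolyte and chemistry events.

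**Step 3: size.** The inputs are treatment-related counts from Table 2.4.2.3-1 (306 patients with solid tumors) and the maximum of 30 patients from section 9.0. The formula is expected patients = 30 × related count / 306.

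- Arthralgia: 15/306 = 4.9%, which agrees with the table's rounded 5%. Expected: 30 × 15/306 = 1.5 patients.
- Back pain, if counted under 8.2.2.7 (an assumption): 30 × 3/306 = 0.3 patients. With arthralgia this makes at most 1.8, reached only if no patient has both.
- Electrolyte events are not in that table, so no count can be given.

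These are any-grade upper bounds: they assume every such case is left off. Treatment-related grade 3-4 arthralgia was 0 of 306 and back pain 1 of 306, so the exposed pain events are almost all low grade.

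**Step 4: fatigue.** It is listed only as a symptom of anemia. Nivolumab fatigue without anemia is not on the list, so it would be lost only if it were filed as an anemia symptom. The ceiling in that case is 30 × 86/306 = 8.4 patients.

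**The case against.** The strongest reply is that the headings are themselves the limit. An event that the investigator attributes to nivolumab is, on a plain reading, neither disease-related nor a symptom of anemia, so it is unexpected and goes on the CRF. This is a fair reading and it reduces the point: the text shows an ambiguity, not a demonstrated exclusion. It does not remove the point, because 8.2 never says that attribution overrides the list, and its two sentences on data entry disagree.

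A second reply is that nothing is lost at source. That stands. The gap is in the CRF, and if the toxicity profile were compiled from medical records it would close. Section 9.0 does not say which will be used.

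It is also fair to say that arthralgia as a sign of an infusion reaction (section 5.1.5) proves little, since infusion reactions are not on the list. The point rests on the related arthralgia in section 2.4.2.3.

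A reader might go further and infer that the toxicity stopping rule is weakened. The rule's printed boundaries and all five printed stopping probabilities reproduce. Suppose monitoring ran on CRF entries alone and every patient with related grade 3-4 fatigue were misfiled and had no other qualifying event (7 of the 52 patients with any related grade 3-4 AE, 13.5%). At a true rate of 0.40, the monitored rate would be 0.40 × (1 − 7/52) = 0.346, and the stopping probability would fall from 0.635 to 0.418. The documents support neither premise: section 9.0 names no data source and has no expectedness filter, and misfiling would depart from the list as worded. If source records are used, the loss is zero.

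**Conclusion.** The point holds in a limited form. Section 8.2 can leave non-serious listed events attributed to nivolumab off the CRF, because it has no explicit exception for them and its two sentences on data entry conflict. CRF data for secondary objective 5 could then be incomplete. The quantifiable part is about 1.5 of 30 patients with related arthralgia. That figure carries a solid-tumor rate over to AML in remission and assumes that every case is omitted. Electrolyte and chemistry events may lack attribution rather than be missing, and fatigue is affected only if misfiled.

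No effect on the stopping rule is shown. Nor do the documents support an inference that hospitalizations for listed events go unreported. Section 8.2.4 says they are not SAEs and the criteria in 8.4 include inpatient hospitalization, but 8.4 later gives hospitalizations for expected events their own route to the supporting company. That is a matter for cross-reference. The whole point calls for a clarifying amendment; no sample size or boundary changes.

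**What to change.** - Amend 8.2 so that every AE attributed to nivolumab is entered on the CRF with grade and attribution, whether or not it is listed.
- Limit the expected-event exemption to events judged unrelated to nivolumab.
- Reconcile the sentence restricting the CRF to unexpected AEs with the unqualified sentence on PDMS/CORe.
- State in section 9.0 that the stopping rule and the toxicity summaries sent after every 3 patients draw on these entries.
- Optionally, cross-reference 8.2.4 and the sentence in 8.4 on hospitalizations for expected events to the hospitalization criterion in 8.4.

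The cost is amended wording and modest extra data entry for at most 30 patients, on events that are already graded and attributed in the medical record.

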8.2.1 Myelosuppression related events (due to disease or leukemia therapy)

8.2.1.1 febrile or infection episodes not requiring management in the intensive care unit

8.2.1.2 epistaxis or bleeding except for catastrophic CNS or pulmonary hemorrhage

8.2.1.3 anemia, neutropenia, lymphopenia, thrombocytopenia, leukopenia

8.2.2 Disease Related Events

8.2.2.1 Symptoms associated with anemia

8.2.2.1.1 fatigue

8.2.2.1.2 weakness

8.2.2.1.3 shortness of breath

8.2.2.2 electrolyte abnormalities (sodium, potassium, bicarbonate, CO₂, magnesium)

8.2.2.3 chemistry abnormalities (LDH, phosphorus, calcium, BUN, protein, albumin, uric acid, alkaline phosphatase, glucose)

8.2.2.4 coagulation abnormalities

8.2.2.5 disease specific therapy (induction, maintenance, salvage, or stem cell therapy)

8.2.2.6 alopecia

8.2.2.7 bone, joint, or muscle pain

8.2.2.8 liver function test abnormalities associated with infection or disease progression

8.2.2.9 disease progression

8.2.2.10 abnormal hematologic values

8.2.3 General Therapy Related Events

8.2.3.1 catheter related events

8.2.3.2 renal failure related to tumor lysis syndrome or antibiotic/ antifungal therapy

8.2.3.3 rash related to antibiotic use

8.2.4 Hospitalization for the management of any of the above expected events (not considered SAE)

8.3 Abnormal hematologic values will not be recorded on the case report form. For abnormal chemical values, the apogee or nadir (whichever is appropriate) will be reported per course on the case report form.

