8.4 Serious Adverse Event Reporting (SAE)

An adverse event or suspected adverse reaction is considered “serious” if, in the view of either the investigator or the sponsor, it results in any of the following outcomes:

- Death
- A life-threatening adverse drug experience – any adverse experience that places the patient, in the view of the initial reporter, at immediate risk of death from the adverse experience as it occurred. It does not include an adverse experience that, had it occurred in a more severe form, might have caused death.
- Inpatient hospitalization or prolongation of existing hospitalization
- A persistent or significant incapacity or substantial disruption of the ability to conduct normal life functions.
- A congenital anomaly/birth defect.
- Pregnancy
- Overdose of investigational agent
- Onset of a new secondary malignancy while on study.

Important medical events that may not result in death, be life-threatening, or require hospitalization may be considered a serious adverse drug experience when, based

upon appropriate medical judgment, they may jeopardize the patient or subject and may require medical or surgical intervention to prevent one of the outcomes listed in this definition. Examples of such medical events include allergic bronchospasm requiring intensive treatment in an emergency room or at home, blood dyscrasias or convulsions that do not result in inpatient hospitalization, or the development of drug dependency or drug abuse (21 CFR 312.32).

- Important medical events as defined above, may also be considered serious adverse events. Any important medical event can and should be reported as an SAE if deemed appropriate by the Principal Investigator or the IND Sponsor, IND Office.
- All events occurring during the conduct of a protocol and meeting the definition of a SAE must be reported to the IRB in accordance with the timeframes and procedures outlined in “The University of Texas M. D. Anderson Cancer Center Institutional Review Board Policy for Investigators on Reporting Unanticipated Adverse Events for Drugs and Devices”. Unless stated otherwise in the protocol, all SAEs, expected or unexpected, must be reported to the IND Office, regardless of attribution (within 5 working days of knowledge of the event).

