- **All life-threatening or fatal events**, that are unexpected, and related to the study drug, must have a written report submitted within **24 hours** (next working day) of knowledge of the event to the Safety Project Manager in the IND Office.
- Unless otherwise noted, the electronic SAE application (eSAE) will be utilized for safety reporting to the IND Office and MDACC IRB.
- Serious adverse events will be captured from the time of the first protocol-specific intervention, until 30 days after the last dose of drug, unless the participant withdraws consent. Serious adverse events must be followed until clinical recovery is complete and laboratory tests have returned to baseline, progression of the event has stabilized, or there has been acceptable resolution of the event.
- Additionally, any serious adverse events that occur after the 30 day time period that are related to the study treatment must be reported to the IND Office. This may include the development of a secondary malignancy.

Reporting to FDA:

- Serious adverse events will be forwarded to FDA by the IND Sponsor (Safety Project Manager IND Office) according to 21 CFR 312.32.

It is the responsibility of the PI and the research team to ensure serious adverse

events are reported according to the Code of Federal Regulations, Good Clinical Practices, the protocol guidelines, the sponsor's guidelines, and Institutional Review Board policy.

Investigator Communication with Supporting Company:

Serious adverse event will be reported by FAX concurrently to Bristol-Myers Squibb (BMS) ([contact]) or BMS email: [contact]. Information not available at the time of the initial report (e.g., an end date for the adverse event or laboratory values received after the report) must be documented on a follow-up report. A final report to document resolution of the SAE is required. Hospitalizations for the management of any expected adverse events (previously described) should be reported to BMS within 5 business days of the event.

Pregnancies: Any pregnancy that occurs during study participation or within 4 weeks of the patient's last study drug administration should be reported to Bristol-Myers Squibb within 24 hours of learning of its occurrence.

The Investigator will follow the pregnant female until completion of the pregnancy. The Investigator will provide this information as a follow-up to the initial SAE.

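### Section 8.2.4 exempts admissions for listed expected events from SAE status with no attribution limit, against section 8.4, so a nivolumab-related admission could miss the IND Office, IRB and FDA

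*Combined protocol and SAP*

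**What the plan says.** Section 8.2 lists events regarded as expected during leukemia therapy and restricts data capture: "Only unexpected AEs will be recorded in the Case Report Form (CRF". The list ends at 8.2.4 with "Hospitalization for the management of any of the above expected events (not considered SAE". Nothing there asks whether the admission is related to nivolumab.

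Section 8.4 defines seriousness by outcome. One outcome is "Inpatient hospitalization or prolongation of existing hospitalization", with no exception and no reference back to 8.2.4. Separate duties follow:

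- **IRB:** every event that occurs during the protocol and meets the SAE definition is reported, under the IRB's own policy.
- **IND Office:** "Unless stated otherwise in the protocol, all SAEs, expected or unexpected, must be reported to the IND Office, regardless of attribution". The time limit is 5 working days after the event becomes known.
- **FDA:** the IND sponsor forwards serious events through its IND Office.
- **Supporting company:** SAEs are reported concurrently, and in addition "Hospitalizations for the management of any expected adverse events (previously described) should be reported to BMS within 5 business days of the event".

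**The concern.** The two sections classify the same admission by different tests. Section 8.2.4 turns on whether the event is on the expected list. Section 8.4 turns on outcome and, for IND Office reporting, sets expectedness and attribution aside. An investigator who follows 8.2.4 as written has no reason to file an SAE for a listed event, even when the drug may have caused it.

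The list is framed around leukemia therapy in general, while this trial gives an anti-PD-1 antibody to patients in remission. Secondary objective 5 is the toxicity profile of nivolumab. At stake is whether the bodies overseeing the IND see every admission that may be due to the study drug, and whether the CRF's adverse event record shows it.

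**Working it through.** The plan gives no figure on this point, so the check is a comparison of text.

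**Step 1. One admission under each section.** Take a patient admitted with thrombocytopenia and non-catastrophic bleeding, not life-threatening, judged possibly related to nivolumab.

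| Question | If 8.2.4 governs | If 8.4 governs |
|---|---|---|
| SAE? | No | Yes |
| IRB | Not as an SAE | Required |
| IND Office | Exempt, through the opening clause of that sentence | Required |
| FDA | Does not enter the route | Handled through the IND Office |
| Supporting company | Within 5 business days | Concurrently, as an SAE |
| CRF adverse event record | Not recorded (8.2) | Not recorded (8.2) |

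The answers differ in every row except the last. The CRF gap comes from 8.2 and is there whichever section governs.

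**Step 2. Reach of the exception clause.** The clause opens the IND Office sentence and qualifies only that sentence. Neither the hospitalization criterion nor the IRB sentence before it carries a similar qualifier. So 8.2.4 can be read as a permitted exception for the IND Office, but not for the definition or the IRB.

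**Step 3. Which listed items exclude nivolumab as a cause?**

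- *Tied to another cause:* fatigue, weakness and shortness of breath (anemia, 8.2.2.1); "liver function test abnormalities associated with infection or disease progression" (8.2.2.8); renal failure (tumor lysis or anti-infective drugs, 8.2.3.2); rash (antibiotics, 8.2.3.3).
- *Not tied:* febrile or infection episodes, bleeding and cytopenias (8.2.1), whose heading attributes them to the disease or to leukemia treatment; electrolyte and chemistry abnormalities (8.2.2.2, 8.2.2.3) and bone, joint or muscle pain (8.2.2.7), which have only a general disease-related heading.

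The 8.2.1 heading does not clearly leave nivolumab out. Section 8.2.2.5 counts maintenance among disease-specific therapies, and section 9.0 describes nivolumab as maintenance therapy.

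**Step 4. Does the protocol expect nivolumab-related forms of the untied items?**

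- Section 5.5 has a provision for drug-related grade 3 thrombocytopenia that is prolonged or accompanied by bleeding.
- Section 5.5 also addresses grade 4 electrolyte abnormalities within its rule for drug-related grade 4 events.
- Table 2.4.2.3-1 reports treatment-related pyrexia in 17/306 = 5.6% and arthralgia in 15/306 = 4.9%, any grade. Treatment-related grade 3-4 counts are 0 for both.

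The table shows only that drug-related forms occur; it does not estimate admissions. The pyrexia match is looser than the others, because 8.2.1 concerns myelosuppression.

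**Step 5. What remains in the CRF.** Section 8.3 keeps abnormal hematologic values off the CRF, but the peak or nadir of abnormal chemistry values is entered per course. A chemistry abnormality would leave a laboratory value, though not an adverse event entry.

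**The case against.** The strongest reply is that the protocol largely reconciles itself. The IND Office sentence allows exceptions stated elsewhere, and 8.2.4 is one. The supporting company is told of these admissions within 5 business days. Death and life-threatening events stay serious, because 8.2.4 exempts hospitalization only. Section 8.4 also lets the principal investigator or the IND Office report any important medical event as an SAE. All of this stands, and it narrows the point. It does not reach the seriousness definition or the IRB sentence, it does not supply an attribution limit, and discretion to report is not a duty to report.

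A reader might infer four stronger things that the documents do not support:

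- **That nivolumab's main immune toxicities are exempt, for example an admission for pneumonitis.** Pneumonitis, colitis, endocrinopathy and infusion reactions are not listed, and shortness of breath is listed only as a symptom of anemia. Drug-induced hepatitis and drug rash fall outside the liver and rash items as worded. Such admissions could be lost only by misattribution.
- **That the toxicity stopping rule is weakened by the exemption.** The rule in section 9.0 counts treatment-related, clinically significant non-hematologic events of grade 3 or higher. Neither SAE status nor hospitalization enters it.
- **That the loss can be sized by scaling any-grade rates from the background study to 30 patients.** Any-grade counts do not measure admissions. Treatment-related grade 3-4 counts in Table 2.4.2.3-1 are 0 for dyspnea, rash, arthralgia and pyrexia, and 7/306 = 2.3% for fatigue.
- **That these admissions go wholly unreported.** The route to the supporting company rules this out.

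**Conclusion.** The point holds in a limited form. Sections 8.2.4 and 8.4 conflict on whether admission for a listed event is an SAE, and the exemption has no attribution limit. For the items not tied to a non-drug cause, following 8.2.4 as written can keep a nivolumab-related admission from the IND Office, IRB and FDA. The 8.2 recording rule can keep it out of the CRF's adverse event record as well.

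No count can be given, because the documents report no hospitalization rate for these events. The zero grade 3-4 treatment-related counts for pyrexia and arthralgia suggest few patients among the 30 planned. Table 2.4.2.3-1 has no thrombocytopenia or electrolyte rows, so the frequency of those is unknown here.

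The conclusion assumes that sites apply 8.2.4 literally, that the discretionary important-medical-event route is not used, and that the IRB policy, which is not among the documents, does not settle the matter. The fix is warranted because it is cheap and concerns safety reporting, not because a large loss has been shown.

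**What to change.** Reconcile 8.2.4 with 8.4 in these places:

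1. In 8.2.4, state that the exemption applies only to admissions judged not related to nivolumab, and that an admission possibly related to nivolumab is reported as an SAE even if the event is listed.
2. In 8.4, add a cross-reference to the limited exemption beside the hospitalization criterion, and state for the IRB, the IND Office and the supporting company whether each receives the exempt admissions and by when.
3. In 8.2, state that possibly related admissions are recorded in the CRF whatever their expectedness.

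This takes a few sentences and does not touch the design or sample size. The cost is a few more SAE reports and CRF entries, chiefly where attribution between the disease and the drug is uncertain.
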